### **GLOSSARY OF ABBREVIATIONS**

AE	Adverse Event
ACT	Asthma Control Test
ATS	American Thoracic Society
B-IPQ	Brief Illness Perceptions Questionnaire
BMQ	Belief in Medicines Questionnaire
CI	Chief Investigator
CYP	Children and Young People
ED	Emergency Department
EMDs	Electronic Monitoring Device/s
ERS	European Respiratory Society
FENO	Fractional Exhaled Nitric Oxide
ICS	Inhaled Corticosteroids
MART	Maintenance and Reliever Therapy
MARS-A	Medication Adherence Report Scale for Asthma
OCS	Oral Corticosteroids
PAPA	Perceptions and Practicalities Approach
PIS	Participant Information Sheet
RCT	Randomised Controlled Trial
REC	Research Ethics Committee
SAR	Serious Adverse Reaction
SAE	Serious Adverse Event
SOP	Standard Operating Procedure
SRBAI	Self-report Behavioural Automaticity Index
TSRQ	Treatment Self-Regulation Questionnaire

### **KEYWORDS**

Financial incentives Electronic monitoring device (EMD) Asthma Adherence Asthma control Children and young people

### **STUDY SUMMARY**

- **TITLE** Financial incentives to improve adherence to inhaled asthma medications in children and young people (CYP) with asthma.
- **DESIGN** Pilot randomised controlled trial (RCT)
  - AIMS To assess the effectiveness of a short-term financial incentives-based intervention at bringing about behaviour change, namely short-medium term improvements in inhaled corticosteroid (ICS) adherence and asthma control in children and young people (CYP) with asthma.

#### **OUTCOME MEASURES Primary outcome:**

Percentage ICS adherence (measured by EMD record of inhaler actuation%)

#### Secondary outcomes:

- Proportion of participants achieving good asthma adherence (≥80%)
- Time to next asthma exacerbation needing a course of oral corticosteroids (OCS)
- Total number of severe exacerbations
- Asthma control (Asthma Control Test, ACT)
- Exhaled nitric oxide (FENO)
- Belief in Medicine Questionnaire (BMQ)
- Brief Illness Perceptions Questionnaire (B-IPQ)
- Habit (self-report behavioural automaticity index, SRBAI)
- Autonomous/controlled motivation (adapted from the Treatment Self-Regulation Questionnaire, TSRQ, for the purpose of this study)
- Self-report adherence (Medication Adherence Report Scale for Asthma, MARS-A)

**POPULATION** CYP aged 11-17 years with an asthma diagnosis

ELIGIBILITY

- CYP aged between 11-17 years old
- A doctor diagnosis of asthma
- Presenting to an emergency department (ED) with a severe exacerbation of asthma (defined by ERS/ATS guidelines\*)
- Own their own smartphone (running Android 8 or higher, or iOS 13 or higher)
- Prescribed maintenance inhaled corticosteroids (ICS) (which can include maintenance and reliever therapy (MART)) for at least 6-months.
- Prescribed one of the following inhalers: Clenil, Flixotide, Symbicort, Seretide.
- **DURATION** Up to 24-weeks (participants will also be involved in a focus group at the end of the study period)

\* Severe exacerbation of asthma: Asthma attack requiring a course of systemic corticosteroids (either prednisolone or dexamethasone), or hospital admission 

Research Governance and Integrity Team

### 1. INTRODUCTION

#### 1.1. BACKGROUND

Approximately 1.1 million United Kingdom (UK) children have asthma, making the disease one of the most common chronic conditions. Asthma can be fatal if poorly managed or uncontrolled and unfortunately, the UK has some of the worst outcomes for asthma. Most children with asthma are prescribed low-dose inhaled corticosteroids (ICS), but not all have good control resulting in persistent and frequent exacerbations of symptoms and escalation of treatment. Poor adherence to medication ICS significantly contributes to poor asthma control. Good adherence is considered >80% but children with asthma often have adherence rates of <50%. Although in some cases ICS is wrongly or over-prescribed providing rational as to why adherence is low, the figures are still concerning and need addressing.

Electronic monitoring devices (EMDs) are not only seen as the 'gold standard' tool for measuring adherence as they electronically record inhaler actuation, but they have also been used as an intervention tool to improve medication adherence. EMDs can be programmed to deliver audio-visual reminders, which often result in improved short-term adherence, but no significant changes to clinical outcomes or sustained behaviour change.

The perceptions and practicalities approach (PAPA) suggests medication adherence can be divided into two fundamental constructs: 1) unintentional adherence (practical factors such as capacity and resources) and 2) intentional adherence (perceptual factors such as motivations and beliefs). Previous EMD interventions have not targeted both unintentional and intentional adherence which could explain the lack of sustained change in adherence.

Additionally, adhering to medication regimes is heavily reliant upon developing a habit. A habit usually forms through the consistent repetition of a desired behaviour until it is performed automatically, without the need for strong intentions to perform the behaviour. Habitual behaviours are important as they are more likely to be sustained over the long term. Rewards may reinforce behaviours, and therefore strengthen habit formation. While there is evidence that autonomous motivation (compared with controlled) is more effective at supporting habit formation, the exact nature of what counts as a reward to support habit formation is not well established. Autonomous motivation refers to being self-motivated compared to controlled motivation which refers to being motivated from external sources.

Therefore, to address the above, it is proposed that adding an additional behavioural strategy, alongside the electronic reminders, may be effective at bringing sustained long-term effects of adherence by successfully targeting the underlying motivations to adhere.

Financial incentives are a widely used behavioural strategy throughout health and research settings. They can help reinforce behaviours and are successful at improving health behaviours in adult populations such as smoking cessation, vaccination uptake and physical activity and at improving medication adherence with for example anti-psychotics, statins, antihypertensive and HIV medications.

Financial incentive studies are limited, but are increasing in children. A narrative review by Kenyon and colleagues discusses design and effectiveness of randomized trials using

Research Governance and Integrity Team

financial incentives to promote healthy behaviours specifically in children. Studies included focused on healthy eating (with interventions delivered within schools), preventing repeat adolescent pregnancies and diabetes management. All studies showed improvements in behaviour change but with mixed results at follow-up assessments.

The use of financial incentives to improve diabetes management is of particular interest because, as with asthma, outcomes are related to medication adherence. One non-randomised study found short-term financial incentives encouraged sustained behaviour change in adolescents with diabetes. A randomised trial with a similar population conducted in 2017 showed improved adherence to self-monitoring compared to controls at 6-month follow-up, yet there was no significant difference in clinical outcomes (HbA1c) at both 3-month and 6-month follow-up. A second randomised trial conducted in 2019, similarly with an adolescent population again showed improved adherence to self-monitoring compared to control but with significantly improved clinical outcomes (HbA1c) at 3-month follow-up.

#### 1.2. RATIONALE FOR CURRENT STUDY

In paediatric asthma, there are currently no randomised trials that explore the effectiveness of using financial incentives for improving medication adherence. A US proof-of-concept study that used electronic reminders coupled with financial incentives improved adherence to asthma medications in 12 African American adolescents. Participants were provided with a smartphone and an EMD (with associated App) to provide visual reminders, positive reinforcement (e.g., shooting a basket game and positive text messages when dose is taken) plus rewards (short-term: accessories to decorate personal app avatar and long-term: 1\$ per inhaler dose). Both adherence and asthma control (measured by the asthma control test ACT) improved across the 8-week period.

Similarly, a feasibility study conducted by ourselves found the use of financial incentives to be feasible and acceptable for improving adherence in paediatric asthma. Adolescents diagnosed with asthma, who had poor medication adherence (<80%) and poor asthma control were recruited from an outpatient asthma clinic. Twelve adolescents were invited to take part and 10 were recruited (7 males, 3 females, 12-16 years) to a 24-week intervention that consisted of eight weeks of electronic reminders and financial incentives related to their adherence (£1 per morning dosage, £1 per evening dosage, capped at £2 per day). Eight out of 10 adolescents provided adherence measurements up to the final study visit. Three adolescents successfully paired their mobile app and EMD up to the final study visit which was associated with improved adherence. The 7 adolescents unable to pair their mobile app and EMD had no change in adherence. Overall, adherence did not significantly change. Exit interviews with adolescents revealed reminders and incentives were welcomed but issues with the technology was frustrating. Adolescents also commented that the intervention was useful by promoting self-monitoring and increasing motivation to take medication.

These findings within asthma warrant the further exploration of this intervention design using financial incentives with the inclusion of a larger sample size and randomisation. In addition, to explore the potential mediators of sustained behaviour change, motivation and the key feature of habit, automaticity, will be tracked in this study.

#### 1.2.1 Hypothesis

The overarching hypothesis of this study is that a short-term intervention consisting of financial incentives will lead to behaviour change and improved ICS adherence and asthma control, in the short-medium term, in CYP with asthma.

### 2. STUDY AIMS AND OBJECTIVES

#### 2.1 Aims

- To assess the effectiveness of a short-term financial incentives-based intervention at bringing about behaviour change and improving ICS adherence and asthma control, in the short-medium term, in CYP with asthma.
- 2. To assess the feasibility of study processes, randomisation, and outcome assessments.
- 3. To generate pilot data that can be used to inform the power calculation and design of a definitive RCT of financial incentives in children with asthma.

#### 2.2 Objectives

- 1. To recruit children and young people aged between 11-17 years with asthma and measure adherence using EMDs (programmed with reminders) and a self-report measure (MARS-A) during a 12-week intervention period when financial incentives are given and compare to a group given an EMD (programmed with reminders) only, and to continue to measure adherence during a subsequent 12-week period (when no financial incentives are given) to assess whether financial incentives lead to continued better adherence in the short-medium term compared to the control group.
- 2. To measure asthma outcomes (number of severe exacerbations, time to exacerbation, asthma symptoms and if feasible given COVID-19 constraints, exhaled nitric oxide) at baseline, 12-weeks, and 24-weeks to assess whether financial incentives lead to short-medium term changes in a range of asthma control measures compared to the control group.
- To measure habit (using the self-report behavioural automaticity index, SRBAI) and autonomous/controlled motivation (using a questionnaire adapted from the Treatment Self-Regulation Questionnaire (TSRQ)) at baseline, 12-weeks, and 24-weeks to

Research Governance and Integrity Team

assess whether financial incentives lead to short-medium term changes in medication taking habits and motivations compared to the control group.

- 4. To measure beliefs in medicine (using Beliefs in Medicines Questionnaire, BMQ) and perceptions of illness (using the Brief-Illness Perceptions Questionnaire, B-IPQ) at baseline, 12-weeks, and 24-weeks to assess whether financial incentives lead to short-medium term changes in beliefs and perceptions regarding medication and illness and compared to the control group.
- 5. To conduct focus groups with participants from both the intervention and the control group and interviews with parents/guardians using a topic guide to obtain feedback of the trial and inform the design of a larger RCT.

Research Governance and Integrity Team

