#### **STUDY VISIT 1:**

Prior to any tests, it will be ensured that all parents/CYP understand all the information provided and have electronically signed the informed consent form.

Participants will be given the Hailie® sensor and shown how to use this, as described above. Participants will be assessed and given guidance on their inhaler technique and will be provided with an Asthma UK children's asthma plan (unless already in receipt of an asthma plan, see appendix for plan) which will be conducted by a clinical research nurse.

The following information will be collected from all CYP; demographics, asthma history, asthma adherence (measured by self-report, MARS-A), asthma control (measured by ACT questionnaire, FENO – which will be measured by the child breathing out slowly though a mouthpiece where the nitric oxide from the breath will be measured the sensor and computer) and behavioural/psychological data (measured by BMQ, B-IPQ, SRBAI, TSRQ-adapted for this study).

Participants will be randomly assigned to either the 1) control group (n=25) or to the 2) financial incentives-based intervention group (n=25). Participants will be told which group they have been randomly assigned to during this visit.

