#### 3.1. STUDY OUTCOME MEASURES

Primary outcome:

• ICS adherence (measured by EMD record of inhaler actuation%)

Secondary outcome:

- Proportion of participants achieving good asthma adherence (≥80%)
- Time to next asthma exacerbation needing a course of oral corticosteroids (OCS)
- Total number of severe exacerbations (incident rate ratio)
- Asthma control (measured by asthma control test (ACT))
- FENO
- Habit (measured by Self-Report Behavioural Automaticity Index, SRBAI)
- Belief in Medicines Questionnaire (BMQ)
- Brief Illness Perception Questionnaire (B-IPQ)
- Autonomous/controlled motivation (adapted from the Treatment Self-Regulation Questionnaire, TSRQ)
- Self-report adherence (Medication Adherence Report Scale for Asthma, MARS-A)

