#### 7.2 Statistical methods and sample size

As this is a pilot study, a formal sample size calculation is not required. However, the estimated sample size of 50 participants in total is based upon a calculation from unpublished adherence data obtained from Royal Brompton Hospital from 400 children. Mean adherence in the sample was 65% (SD 22%). A Cochrane review of adherence interventions to ICS for asthma found that electronic trackers or reminders led to better adherence of 19% (95% CI 14.47 to 25.26). Based upon this information, to give 80% power to achieve a 19% difference between the intervention group and controls, 21 participants are required per group. The target of 25 per group accounts for participant dropout. This is supported by evidence that as a pilot study, 25 participants per group, with a total of 50 participants is sufficient.

Data analysis will be conducted using the Statistical Package for the Social Services (SPSS). Statistical analysis of quantitative, normally distributed data will be reported with means ± standard deviations (SD) and non-parametric data will be reported as medians with interquartile range. Data will be tested for normality using visual inspection, histograms, and Kolmogorov-Smirnov testing. Parametric tests will be used where possible for normally distributed data and logarithmically transformed data, otherwise appropriate non-parametric tests shall be used. The significance levels for all tests will be set at <0.5.

Categorical data will be reported as proportions. Comparative analysis of variance between 2 groups for continuous data will be performed using the student's t test for normally distributed data and the Mann Whitney U tests for non-normally distributed data and for more than 2 groups the ANOVA or Kruskal Wallis respectively. A comparison of the proportions between groups will be performed using the Pearson Chi 2 tests. Within group analysis the ANOVA test will also be used.

Questionnaire data will be used alongside group comparisons to observe any notable changes or differences between groups.

Qualitative data obtained from the focus groups will be thematically analysed. An independent researcher will aid with the facilitation/analysis of qualitative aspect of the study to ensure there is no bias.

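### The hypothesis claims effectiveness on asthma control, but the documents disagree on its measure, name no deciding visit and test every secondary at one common level without calling them exploratory

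*Combined protocol and SAP*

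**What the plan says.** Section 1.2.1 predicts that the intervention "will lead to behaviour change and improved ICS adherence and asthma control, in the short-medium term, in CYP with asthma". Aim 1 in section 2.1 is "To assess the effectiveness of a short-term financial incentives-based intervention" on both adherence and asthma control. Adherence has the single primary outcome. Asthma control is described in three ways:

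- Section 3.1 lists "Asthma control (measured by asthma control test (ACT" as one secondary, with FENO and the two exacerbation outcomes as separate entries.
- Section 3, Study Visit 1, records "asthma control (measured by ACT questionnaire, FENO" together.
- Objective 2 in section 2.2 covers severe exacerbations, time to exacerbation, symptoms and, if feasible, "exhaled nitric oxide) at baseline, 12-weeks, and 24-weeks", in order "to assess whether financial incentives lead to short-medium term changes in a range of asthma control measures compared to the control group".

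Section 3.1 lists ten unranked secondaries and gives none of them an analysis time point. In section 7.2, the sentence "The significance levels for all tests will be set at" ends with the printed value <0.5. On the questionnaires, that section adds: "Questionnaire data will be used alongside group comparisons to observe any notable changes or differences between groups". It gives no order of testing, key secondary or multiplicity rule, and it does not describe the secondaries as exploratory.

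Three statements elsewhere bear on the point. Section 1.2 says that motivation and automaticity are tracked to explore possible mediators. Section 3 says that FENO is dropped as a secondary if visits are remote. The study describes itself throughout as a pilot.

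**The concern.** Asthma control is the second half of the stated hypothesis, yet the reader cannot tell which result would settle it. ACT could improve at 12 weeks while exacerbations are unchanged at 24 weeks, and the plan does not say which of these answers the question. Objectives 3 and 4 make the same comparison with control for habit, motivation, beliefs and illness perceptions, again at two visits.

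With several measures, two visits and one level for every test, nothing in the plan prevents an isolated significant secondary from being reported as evidence of effectiveness. Participants know their arm, and ACT and the questionnaires are self-reported, so a deciding measure fixed in advance is worth having. Aim 3 uses the results to plan a definitive trial.

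**Working it through.** **Which level was intended.** Section 7.2 gives 80% power, a difference of 19 points, an SD of 22 and 21 per group. By the normal approximation, n = 2(z_α + z_β)² × SD² / difference².

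- Two-sided 0.05: 2 × (1.960 + 0.842)² × 22² / 19² = 21.05, so 21 to the nearest whole number (22 if rounded up). Power at 21 per group is 79.9%.
- One-sided 0.05 gives 17 per group.
- The printed 0.5 gives 7 per group.

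Only two-sided 0.05 reproduces the plan's figure, so it is used below.

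**How many tests.** The documents do not state this, so these counts are assumptions.

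- Asthma control as in section 3.1: ACT at 12 and 24 weeks = 2.
- Objective 2 without FENO: ACT at two visits, exacerbation count once, time to exacerbation once = 4.
- Objective 2 with FENO at two visits: 4 + 2 = 6.
- All ten secondaries: eight outcomes at two visits plus the two exacerbation outcomes once each = 16 + 2 = 18.

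Separate scores for the motivation or belief subscales would add tests. Section 7.2 names no time-to-event or count method, so one test for each exacerbation outcome is also assumed.

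**Chance of at least one false positive when there is no true effect.** For m independent tests this is 1 − 0.95^m; for example, 1 − 0.95^6 = 26%. For test statistics that are jointly normal with common correlation ρ, it is 1 − ∫[Φ((1.96 − c√ρ)/√(1 − ρ)) − Φ((−1.96 − c√ρ)/√(1 − ρ))]^m φ(c) dc. Counting only results that favour incentives removes the second Φ term. The documents give no correlations, so a range is shown.

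| Tests | ρ = 0 | ρ = 0.5 | ρ = 0.8 | Favouring incentives only, ρ = 0.5 |
|---|---|---|---|---|
| 2 (ACT) | 10% | 9% | 8% | 5% |
| 4 (no FENO) | 19% | 16% | 11% | 8% |
| 6 (with FENO) | 26% | 21% | 14% | 10% |
| 18 (all secondaries) | 60% | 40% | 22% | 20% |

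The reference value for a single test is 5%, or 2.5% counting only results that favour incentives.

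**What a single deciding measure can detect.** A two-sided t test at 0.05 has 80% power for a difference of 0.81 SD with 25 per arm, or 0.89 SD with 21. A Bonferroni split over ten secondaries (0.005 each) raises this to 1.08 SD with 25 per arm.

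**The case against.** This is a 50-participant pilot with one declared primary, and only that primary is sized. Section 3.1 does attach asthma control to ACT, and on that definition the chance of a false positive is only about 9%. FENO may not be collected. Section 1.2 presents habit and motivation as exploratory, and the questionnaire sentence in section 7.2 can fairly be read as descriptive.

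All of this stands and limits the size of the point. It does not remove it. ACT is one unranked entry with no visit attached, objective 2 and the visit descriptions use the term more widely, and the remark in section 1.2 does not reach asthma control. A pilot may leave its secondaries exploratory, but this one does not say so and states an effectiveness hypothesis.

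Four stronger readings are tempting and are not supported:

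- That a chance positive is likely. At correlation 0.5 the figures run from 9% to 40%. The 60% needs 18 uncorrelated tests, which is implausible for the same instruments used twice in the same children.
- That the plan has no measure of asthma control. It has several definitions that need reconciling.
- That the plan lets any one small p value establish improved asthma control. No section states such a rule; the plan is silent on what decides.
- That tests will really be run at 0.5. Ten independent tests at that level would give a false positive 99.9% of the time, but the sample size points to 0.05 and the value looks like a misprint.

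**Conclusion.** The point holds as an inconsistency and an omission of moderate size. The effectiveness claim on asthma control has no agreed measure and no deciding visit, and all secondaries share one significance level without an exploratory label. The false-positive chance is about two to four times the nominal 5% for asthma control (9% to 21%) and about eight times for all secondaries (40%, range 22% to 60%). These figures rest on a per-test level of two-sided 0.05, on an assumed correlation of 0.5, and on the test counts set out above.

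A reader might infer that a formal multiplicity correction is required. It is not: in a pilot of this size it would cost more power than labelling does, and estimates with intervals serve Aim 3 better. Nor do the documents show that a chance result would set the endpoint of the definitive trial; Aim 3 refers only to its power calculation and design.

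**What to change.** In section 7.2:

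- State that effectiveness is concluded only from electronically monitored adherence over one named analysis period. No period is given at present, and objective 1 spans both 12-week periods.
- Correct the printed significance level and state whether it is two-sided.
- State that all secondaries are exploratory, reported as between-arm estimates with 95% confidence intervals and with no claim of effect based on a p value. Replace the questionnaire sentence to match.

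In sections 1.2.1 and 2.1 and in objective 2, reword the asthma-control part as 'to estimate'.

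If the sponsor prefers to keep an asthma-control hypothesis, reconcile objective 2 and the visit descriptions with section 3.1. Then name one measure at one visit, and test it only after a significant primary whose period has been defined.

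The cost is wording before analysis, with no extra participants, visits or data. The downside is that an isolated significant secondary can no longer be reported as evidence of effectiveness.
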